# 9.1.6. Organs at risk

Dose constraints for organs at risk should be in accordance with local policy.

# 9.1.7. Radiotherapy treatment scheduling and gaps

A gap of up to 3 days is acceptable in the event of machine service or breakdown. If the treatment machine is unavailable for more than 3 days, please contact the RE-ARM trial manager.

## 9.1.8. Palliative radiotherapy

Participants in both groups are permitted to received palliative radiotherapy following trial entry if clinically indicated. This should be reported on the appropriate CRF.

#### 9.2. Atezolizumab

#### 9.2.1. IMP dose and schedule

Atezolizumab should be started within 2 weeks following randomisation. Sites must use the RE-ARM allocated atezolizumab stock provided.

Atezolizumab is administered intravenously over 30 to 60 minutes at a dose of 1200mg on a 21 day cycle, until loss of clinical benefit or unmanageable toxicity. The infusion is not intended to be administered via push or bolus.

## 9.2.2. IMP prescription and dispensing

Atezolizumab should be prescribed by the Principal Investigator or delegated clinician using the specific RE-ARM prescription and dispensed by the hospital pharmacy using RE-ARM allocated atezolizumab stock.

Atezolizumab should be prepared by a healthcare professional in accordance with the pharmacy guidance notes. Preparation should be:

- Performed under aseptic conditions by trained personnel in accordance with good practice rules, especially with respect to the aseptic preparation of parenteral products.
- Prepared in a laminar flow hood or biological safety cabinet using standard precautions for the safe handling of intravenous agents.
- Followed by adequate storage of the prepared solution for intravenous infusion to ensure maintenance of aseptic conditions.

Do not shake. Twenty mL of atezolizumab concentrate should be withdrawn from the vial and diluted into a polyvinal chloride (PVC), polyolefin (PO), polyethylene (PE) or polypropylene (PP) infusion bag containing sodium chloride 9 mg/mL (0.9%) solution for injection. After dilution, the final concentration of the diluted solution should be between 3.2 and 16.8 mg/mL. The bag should be gently inverted to mix the solution in order to avoid foaming. Chemical and physical in-use stability has been demonstrated for up to 24 hours at  $\leq$  30 °C and for up to 30 days at 2 °C to 8 °C from the time of preparation. For microbiological control purposes it is recommended that the prepared infusion should be administered immediately or no longer than 24 hours after preparation at 2 °C to 8 °C or 8 hours at ambient temperature ( $\leq$  25 °C), unless dilution has taken place in controlled and validated aseptic conditions.

## 9.2.3. Patient cards

Small wallet sized cards can be produced by ICR-CTSU on request by the participating site. Each card will state:

- The name of the participating site
- That the patient is participating in the RE-ARM trial

- That the patient is taking atezolizumab
- An emergency contact number for the participating site

#### 9.2.4. Duration of atezolizumab treatment

Participants will receive treatment until loss of clinical benefit or unmanageable toxicity up to a maximum of two years after starting RE-ARM allocated atezolizumab.

# 9.2.5. Supportive care

Supportive care should be given in accordance with the current summary of product characteristics and local policy.

# 9.2.6. Concomitant therapy

All medication considered necessary for the participants' welfare and which is not expected to interfere with the evaluation of the study drugs may be given at the discretion of the investigator. All concomitant medications must be recorded in the patient's notes, as well as the appropriate pages of the CRF.

Systemic corticosteroids or other immunosuppressants can be used to treat immune-related adverse reactions after starting atezolizumab. Atezolizumab dosing should be delayed until complete withdrawal of immunosuppressants and reduction of corticosteroids to  $\leq$  10 mg prednisolone or equivalent per day.

# 9.2.7. Non-permissible medications/therapies

No formal pharmacokinetic drug interaction studies have been conducted with atezolizumab. Since atezolizumab is cleared from the circulation through catabolism, no metabolic drug-drug interactions are expected.

Use of concomitant cytotoxic chemotherapy is not permitted during study treatment.

Use of live-attenuated vaccines is not permitted during study treatment (use of inactivated vaccines for prophylaxis is permitted).

#### 9.2.8. Dose modifications – atezolizumab

Atezolizumab dose reductions are not recommended. Recommended treatment modifications in the case of adverse reactions are detailed below.

Immune related adverse reaction	Severity (NCICTCAE v5)	Treatment modification
Pneumonitis	Grade 1	Consider treatment delay, monitor every 2-3 days
	Grade 2	Withhold atezolizumab
		Treatment may be resumed when the event improves to Grade 0 or Grade 1 within 12 weeks, and corticosteroids have been reduced to ≤ 10 mg prednisolone or equivalent per day
	Grade 3 or 4	Permanently discontinue atezolizumab
Hepatitis	Grade 2:	Withhold atezolizumab

Immune related adverse reaction	Severity (NCICTCAE v5)	Treatment modification
	(ALT or AST > 3 to 5 x upper limit of normal [ULN] or blood bilirubin > 1.5 to 3 x ULN)	Treatment may be resumed when the event improves to Grade 0 or Grade 1 within 12 weeks and corticosteroids have been reduced to ≤ 10 mg prednisolone or equivalent per day
	Grade 3 or 4:	Permanently discontinue atezolizumab
	(ALT or AST > 5 x ULN	Consider hepatology referral
	or	
	blood bilirubin > 3 x ULN)	
Colitis	Grade 2 or 3 diarrhoea	Withhold atezolizumab
	<pre>(increase of ≥ 4 stools/day over baseline) or Symptomatic colitis</pre>	Treatment may be resumed when the event improves to Grade 0 or Grade 1 within 12 weeks and corticosteroids have been reduced to ≤ 10 mg prednisolone or equivalent per day  Consider gastroenterology referral
	Grade 4 diarrhoea or colitis (life threatening; urgent intervention indicated)	Permanently discontinue atezolizumab
Hypothyroidism or	Symptomatic	Withhold atezolizumab
hyperthyroidism		Hypothyroidism:
		Treatment may be resumed when symptoms are controlled by thyroid replacement therapy and TSH levels are decreasing
		Hyperthyroidism:
		Treatment may be resumed when symptoms are controlled by anti-thyroid medicinal product and thyroid function is improving
		Consider endocrinology referral
Adrenal insufficiency	Symptomatic	Withhold atezolizumab
		Treatment may be resumed when the symptoms improve to Grade 0 or Grade 1 within 12 weeks and corticosteroids have been reduced to ≤ 10 mg prednisolone or equivalent per day and patient is stable on replacement therapy
		Consider endocrinology referral

Immune related adverse reaction	Severity (NCICTCAE v5)	Treatment modification		
Hypophysitis	Grade 2 or 3	Withhold atezolizumab		
		Treatment may be resumed when the symptoms improve to Grade 0 or Grade 1 within 12 weeks and corticosteroids have been reduced to ≤ 10 mg prednisolone or equivalent per day and patient is stable on replacement therapy		
		Consider endocrinology referral		
	Grade 4	Permanently discontinue atezolizumab		
Type 1 diabetes	Grade 3 or 4 hyperglycaemia	Withhold atezolizumab		
mellitus	(fasting glucose > 250 mg/dL or 13.9 mmol/L)	Treatment may be resumed when metabolic control is achieved on insulin replacement therapy		
Infusion-related reactions	Grade 1 or 2	Reduce infusion rate or interrupt. Premedication with antipyretic and antihistamines may be considered.		
		Treatment may be resumed when the event is resolved		
	Grade 3 or 4	Permanently discontinue atezolizumab		
Rash	Grade 3	Withhold atezolizumab		
		Treatment may be resumed when rash is resolved and corticosteroids have been		
		reduced to ≤ 10 mg prednisolone or		
		equivalent per day		
	Grade 4	Permanently discontinue atezolizumab		
Myasthenic syndrome/myasthenia gravis, Guillain-Barré syndrome and Meningoencephalitis	All grades	Permanently discontinue atezolizumab		
Pancreatitis	Grade 3 or 4 serum amylase	Withhold atezolizumab		
	or lipase levels increased (> 2 x ULN)  or  Grade 2 or 3 pancreatitis	Treatment may be resumed when serum amylase and lipase levels improve to Grade 0 or Grade 1 within 12 weeks, or symptoms of pancreatitis have resolved, and corticosteroids have been reduced to ≤ 10 mg prednisolone or equivalent per day		

Immune related adverse reaction	Severity (NCICTCAE v5)	Treatment modification
	Grade 4 or any grade of recurrent pancreatitis	Permanently discontinue atezolizumab
Myocarditis	Grade 2	Withhold atezolizumab
		Treatment may be resumed when the symptoms improve to Grade 0 or Grade 1 within 12 weeks and corticosteroids have been reduced to ≤ 10 mg prednisolone or equivalent per cay
	Grade 3 and 4	Permanently discontinue atezolizumab
Nephritis	Grade 2:	Withhold atezolizumab
	(creatinine level > 1.5 to 3.0 x baseline or > 1.5 to 3.0 x ULN)	Treatment may be resumed when the event improves to Grade 0 or Grade 1 within 12 weeks and corticosteroids have been reduced to ≤ 10 mg prednisolone or equivalent per day
	Grade 3 or 4:	Permanently discontinue atezolizumab
	(creatinine level > 3.0 x baseline or > 3.0 x	,
Myositis	Grade 2 or 3	Withhold atezolizumab
	Grade 4 or grade 3 recurrent myositis	Permanently discontinue atezolizumab
Other immune-related adverse reactions	Grade 2 or Grade 3	Withhold until adverse reactions recovers to Grade 0-1 within 12 weeks, and corticosteroids have been reduced to $\leq$ 10 mg prednisolone or equivalent per day.
	Grade 4 or recurrent Grade 3	Permanently discontinue atezolizumab (except endocrinopathies controlled with replacement hormones)

# 9.2.9. Missed doses

If a planned dose of atezolizumab is missed it should be administered as soon as possible; it is recommended not to wait until the next planned dose. The schedule of administration should be adjusted to maintain a 3-week interval between doses. If a patient does not receive atezolizumab for more than 12 weeks trial treatment should be discontinued.

## 9.2.10. Overdoses

There is no information on overdose with atezolizumab.

In case of overdose, patients should be closely monitored for signs or symptoms of adverse reactions, and appropriate symptomatic treatment instituted.

## 9.2.11. Discontinuation and subsequent therapy

Atezolizumab should be discontinued if patients are no longer deriving clinical benefit or in the case of severe toxicity (see section 9.6). Further treatment will be at the local clinician's discretion.

## 9.2.12. Supply and distribution

Atezolizumab is manufactured and provided free of charge by Roche to participating sites for use following participants' randomisation.

Roche are responsible for distribution of atezolizumab to participating sites, as detailed in the pharmacy guidance notes.

No drug will be distributed to participating centres unless ICR-CTSU is satisfied that the required approvals and agreements and initiation procedures are complete.

## 9.2.13. Formulation, packaging, storage conditions and labelling

Atezolizumab is provided as a concentrate for solution for infusion. Each 20 mL vial of concentrate contains 1,200 mg atezolizumab. Vials should be stored in a refrigerator (2  $^{\circ}$ C – 8  $^{\circ}$ C) and should not be frozen. Vials should be stored in the outer carton in order to protect from light.

The participating site is responsible for segregating atezolizumab supplied by Roche from other hospital stock in a dedicated area stating that the stock is for RE-ARM study. At the time of dispensing it is the responsibility of the site to comply with Annex 13 labelling requirements for the final IV infusion prior to administration.

# 9.2.14. Pharmacy responsibilities and drug accountability

After randomisation participants should receive RE-ARM allocated atezolizumab stock. The study drug must not be used for treatment of patients who are not randomised RE-ARM participants.

Records must be kept of all deliveries, dispensing and destruction in accordance with the RE-ARM Pharmacy Guidance Notes. These records may be requested by ICR-CTSU during the trial to monitor supply and usage of stock. Account must be given of any discrepancies and certificates of delivery and return must be signed.

# 10. RADIOTHERAPY QUALITY ASSURANCE (QA)

No trial specific radiotherapy quality assurance process is required. All participating sites will be asked to confirm prior to activation that they have received a recent independent dosimetry audit.

#### 11. PHARMACOVIGILANCE

#### 11.1. Definitions

# 11.1.1. Adverse Event (AE)

An AE is any untoward medical occurrence in a patient or clinical trial participant administered an investigational medicinal product; the event does not necessarily have a causal relationship with the treatment or usage.

#### 11.1.2. Special situations

The following special situations should be reported in accordance with section 11.3 even in the absence of an AE:

 Data related to on-study atezolizumab usage during pregnancy or breastfeeding (see section 11.8), data related to overdose, abuse, misuse or medication error (including potentially exposed or intercepted medication errors)

Accidental overdose and medication error, are defined as follows:

- Accidental overdose: accidental administration of a drug in a quantity that is higher than the assigned dose
- Medication error: accidental deviation in the administration of the drug. In some situations, a medication error may be intercepted prior to administration of the drug.

Special situations are not in themselves adverse events, but may result in adverse events. Each adverse event associated with a special situation should be recorded separately on the Adverse Event eCRF. If the associated adverse event fulfils seriousness criteria then they should be reported as SAEs in accordance with section 11.3.

# 11.1.3. Product complaints

A product complaint is any written or oral information received from a complainant that alleges deficiencies related to identity, quality, safety, strength, purity, reliability, durability, effectiveness, or performance of a product after it has been released and distributed to the commercial market or clinical trial. Product complaints related to the study drug should be reported in accordance with section 11.3.

# 11.1.4. Adverse Events of Special Interest (AESIs)

AEs experienced by any patient receiving study atezolizumab which meet any of the criteria listed below are considered AESIs, and should be reported to the ICR-CTSU within the same timeframe as SAEs, as detailed in Section 11.3:

- Autoimmune haemolytic anaemia
- Cytokine-release syndrome
- Grade ≥2 cardiac disorders (e.g. atrial fibrillation, myocarditis, pericarditis)
- Hypersensitivity
- Immune-related adrenal insufficiency
- Immune-related colitis
- Immune-related diabetes mellitus
- Immune-related Guillan-Barré syndrome
- Immune-related hepatitis including AST or ALT >10 x ULN
- Immune-related hyperthyroidism
- Immune-related hypophysitis
- Immune-related meningoencephalitis
- Immune-related Myasthenic Syndrome / Myasthenia Gravis
- Immune-related myocarditis
- Immune-related myositis
- Immune-related nephritis
- Immune-related ocular inflammatory toxicity
- Immune-related pancreatitis
- Immune-related pneumonitis
- Immune-related severe cutaneous reaction
- Immune-related vasculitis
- Influenza-like illness

27

- Infusion-related reactions
- Rhabdomyolysis
- Systemic immune activation
- Systemic inflammatory response syndrome
- Systemic lupus erythematosus

If any AESI also meets the definition of an SAE, an SAE report should be completed and submitted together with the AESI form.

## 11.1.5. Serious Adverse Event (SAE)

An SAE is any untoward medical occurrence that occurs after the commencement of study treatment and within 90 days following the last administration and:

- Results in death,
- Is life-threatening
- Requires hospitalisation or prolongation of existing inpatients' hospitalisation
- Results in persistent or significant disability or incapacity
- Is a congenital anomaly or birth defect

Important adverse events that are not immediately life-threatening or do not result in death or hospitalisation but may jeopardise the participant or may require intervention to prevent one of the other outcomes listed in the definition above, may also be considered serious.

Progression of the indicated disease and death due to progression of the indicated disease are not considered SAEs.

Pregnancy or aid in the conception of a child whilst participating in a trial is not itself considered an SAE but should be followed up for congenital anomalies or birth defects.

#### 11.1.6. Serious Adverse Reaction (SAR)

A serious adverse reaction is an SAE that is suspected as having a causal relationship to the investigational medicinal product, as assessed by the investigator responsible for the care of the patient. A suspected causal relationship is defined as possibly, probably or definitely related (see definitions of causality table).

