## 1.4. Known risks and benefits of immunotherapy in combination with radiotherapy

In a human context, a number of case reports in a range of cancers, particularly in melanoma and non-small cell lung cancer, describe remarkable systemic responses to radiotherapy when given during immune modulatory treatment(23-28). The combination of anti PD1-based immunotherapy and palliative hypofractionated radiotherapy appears to be well tolerated by patients(29). In a recent meta-analysis of 16 studies which included 451 patients with metastatic melanoma treated with radiotherapy and the CTLA-4 inhibitor, ipilimumab, an abscopal effect was reported in 26.5% patients (median effect across 8 studies that quantified the abscopal response rate) and median overall survival was 19 months(30). In a non-randomised study of 39 heavily pre-treated patients with metastatic non-small cell lung cancer receiving radiotherapy and ipilimumab, a radiological response rate of 33% was seen in evaluable patients. Adverse events were typical of ipilimumab and were not increased with the addition of radiotherapy.

In metastatic urothelial carcinoma, a phase I study assessed 3 x 8Gy administered either just before the first cycle of pembrolizumab or just before the third cycle(22). This study showed acceptable toxicity profiles with no dose limiting toxicities and only one grade three treatment-related adverse event. In addition, in this small study, encouraging clinical responses were seen in the cohort receiving radiation just before the third cycle of pembrolizumab. The PLUMMB study investigated 36Gy/6 fractions administered to the whole bladder in combination with pembrolizumab. Significant toxicity occurred with this dose fractionation with three out of five patients experiencing grade 3 bladder toxicity and a further patient experiencing grade 3 bowel toxicity(31). As a consequence, the trial design has been amended with a reduction in total radiotherapy dose to 30Gy/5 fractions. Collectively, these studies indicate that radiation administered in combination with immune checkpoint blockade is worthy of further study in bladder cancer. However, careful choice of radiotherapy fractionation schedules is necessary to achieve induction of type 1 interferon yet avoid dose-limiting toxicity, particularly in the pelvis.

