#### 9. TRIAL TREATMENT

All participants will receive atezolizumab, the investigational medicinal product within RE-ARM. Participants in the atezolizumab plus radiotherapy group will also receive radiotherapy to the primary site or a metastatic lesion.

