# 11.1.7. Definitions of causality

Relationship	Description
Unrelated	There is no evidence of any causal relationship with the trial treatment
Unlikely	There is little evidence to suggest there is a causal relationship (e.g. The event
	did not occur within a reasonable time after administration of the trial
	medication). There is another reasonable explanation for the event (e.g. The
	patient's clinical condition, other concomitant treatment)
Possible	There is some evidence to suggest a causal relationship (e.g. Because the event
	occurs within a reasonable time after administration of the trial medication).
	However, the influence of other factors may have contributed to the event (e.g.
	The patient's clinical condition, other concomitant treatments)
Probable	There is evidence to suggest a causal relationship, and the influence of other
	factors is unlikely
Definitely	There is clear evidence to suggest a causal relationship, and other possible
	contributing factors can be ruled out
Not assessable	There is insufficient or incomplete evidence to make a clinical judgement of the
	causal relationship.

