# 11.1.8. Suspected Unexpected Serious Adverse Reaction (SUSAR)

A serious adverse reaction, the nature or severity of which is not consistent with the safety information provided in the applicable Summary of Product Characteristics (SmPC), and is assessed as unexpected by the Chief Investigator.

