## 11.3. Reporting SAEs, AESIs, special situations and product complaints to ICR-CTSU

Any SAE, AESI, occurring after the commencement of study treatment and up to 90 days following the last dose of study drug must be reported. Special situation or product complaints should be reported when the investigator becomes aware of the incident.

Any SAEs that occur more than 90 days after the last dose of study drug that, in the opinion of the Principal Investigator, are related to the study drug should be reported to ICR-CTSU if the Principal Investigator becomes aware of them.

All SAEs, AESIs, special situations or product complaints should be reported to ICR-CTSU within 24 hours of the Principal Investigator (or designated representative) becoming aware of the event, by completing the relevant RE-ARM SAE/AESI/other incident form (as applicable).

SAE reports should be sent to:

The ICR-CTSU safety desk

[contact]

copying [contact]

For the attention of the RE-ARM Trial team

As much information as possible, including the Principal Investigator's assessment of causality for SAE reports, must be reported to ICR-CTSU in the first instance. Additional follow up information should be reported as soon as it is available.

All SAE forms must be completed, signed and dated by the Principal Investigator or designated representative. All reported SAEs will be forwarded to Roche by ICR-CTSU.

All reported AESIs, special situations and product complaints should be sent to [contact] and will be forwarded to Roche following receipt at ICR-CTSU.

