#### 11.4. Review of serious adverse events

The Chief Investigator (or designated representative) will assess all reported SAEs for causality and expectedness (NB. The Chief Investigator cannot down-grade the Principal Investigator's assessment of causality.)

SAEs assessed as having a causal relationship to study drug and as being unexpected (SUSARs) will undergo expedited reporting to the relevant authorities and all other interested parties by ICR-CTSU (see 11.5).

Sites should respond as soon as possible to requests from the Chief Investigator or designated representative (via ICR-CTSU) for further information that may be required for final assessment of an SAE.

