# 11.5. Expected Radiotherapy Adverse Events

The following adverse event will be classed as expected within the RE-ARM trial if they are assessed as being related to radiotherapy: fatigue; nausea/vomiting; diarrhoea; skin irritation/reaction; skin atrophy; mucositis; gastritis; colitis; shortness of breath; dysurea frequency.

The above listed events should be reported within the trial CRF database and under the reporting timeframes given for SAEs above if it meets the relevant reporting criteria.

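### Serious-reaction and late-SAE rules refer to atezolizumab, although radiotherapy is the randomised intervention, and the radiotherapy expectedness list conflicts with the severity test for SUSARs

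*Protocol*

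**What the plan says.** Section 9 of the protocol identifies the drug under test: "All participants will receive atezolizumab, the investigational medicinal product within RE-ARM". Section 12.2 randomises patients to continue atezolizumab with or without radiotherapy.

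The safety rules then use several different terms for the cause of an event:

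- Section 11.1.6: "A serious adverse reaction is an SAE that is suspected as having a causal relationship to the investigational medicinal product".
- Section 11.1.7 grades causality on a different basis. Its lowest category reads "There is no evidence of any causal relationship with the trial treatment".
- Section 11.1.8 defines a SUSAR as a serious adverse reaction, "the nature or severity of which is not consistent with the safety information" in the Summary of Product Characteristics.
- Section 11.4 sends an SAE for expedited reporting only if it is both related to study drug and unexpected.
- Section 11.5 lists events, including colitis, diarrhoea, gastritis and shortness of breath, that "will be classed as expected within the RE-ARM trial if they are assessed as being related to radiotherapy". It gives no grade, seriousness or outcome limit, but says listed events follow the SAE timeframes when they meet the reporting criteria.
- Section 11.3 has every SAE up to 90 days after the last dose of study drug sent within 24 hours. Beyond 90 days, only SAEs that in the Principal Investigator's opinion "are related to the study drug should be reported to ICR-CTSU".
- Figure 3 asks whether the investigators suspect that the SAE is related, without saying to what.

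**The concern.** Because both arms receive atezolizumab, harm that differs between the arms will come from radiotherapy or from its combination with the drug. The rules for escalation and for late capture are nevertheless written around the drug. Three things are at stake:

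- whether an unexpected serious event blamed on radiotherapy reaches the regulator and ethics committee on the 7- or 15-day clock of section 11.6;
- whether a severe event blamed on both treatments can be labelled expected simply because its name is on a list;
- whether late serious radiotherapy effects are reported at all.

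Section 1.5 makes the case for the combination conditional on little added toxicity, and section 9.1.1 allows the bladder as a target, so these events bear on the trial's conclusion.

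**Working it through.** No statistical figure is involved. The check sets the sections side by side and adds a day count.

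**1. Event attributed to radiotherapy alone, inside the window.** It is an SAE, because section 11.1.5 is neutral on cause. It is not a serious adverse reaction under 11.1.6, because the suspected cause is not the IMP. It therefore cannot be a SUSAR under 11.1.8, and it fails the study-drug condition in 11.4. The clocks in 11.6 apply only to SUSARs, so on these definitions there is no expedited route. Section 11.1.7 (trial treatment), Figure 3 (related, unqualified) and 11.5 (expectedness for radiotherapy-related events) suggest that such events were meant to be in the scheme. An expectedness list has little purpose for events that cannot become SUSARs. A further sign of incomplete editing is that 11.4 points to 11.5 for expedited reporting, which is actually in 11.6.

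**2. Event attributed to both treatments.** Take a life-threatening colitis. Colitis is on the 11.5 list, so that section classes it as expected. Under 11.1.8 its severity could make it unexpected against the drug's product information. No rule says which section prevails. Dual attribution is foreseeable, because immune-related colitis is also an event of special interest in 11.1.4.

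**3. Late events.** Inputs: first on-study dose on day 1; 21-day cycles (9.2.1); radiotherapy completed before cycle 2 (9.1.2), so by day 21 on the nominal schedule; a window of 90 days after the last dose (11.3); up to 34 cycles (8.10).

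Closing day after *c* cycles = 1 + 21 × (*c* − 1) + 90. Time since the last fraction = closing day − 21.

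| Cycles given | Last dose | Window closes | Days after a last fraction on day 21 |
|---|---|---|---|
| 1 | day 1 | 1 + 90 = day 91 | 91 − 21 = 70 |
| 3 | day 43 | 43 + 90 = day 133 | 133 − 21 = 112 |
| 34 | day 694 | 694 + 90 = day 784 | 784 − 21 = 763 |

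If radiotherapy instead finished on day 5 (an assumption: five consecutive days from day 1), the one-dose figure is 91 − 5 = 86 days.

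Section 11.1.5 counts its 90 days from the last administration, in a sentence about study treatment. If a fraction on day 21 counts, the one-dose window closes on day 21 + 90 = 111. From cycle 2 onward the last administration is atezolizumab on either reading.

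After closure, a serious event attributed to radiotherapy alone has no reporting rule. Post-treatment toxicity monitoring in 8.8 covers immune-related toxicity only. The length of radiotherapy safety capture is thus set by how long atezolizumab lasts, not by when radiotherapy was given.

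**The case against.** The strongest reply is that tying serious reactions and SUSARs to the IMP is a definition a protocol may adopt, and that little is lost in practice. Within the window every SAE, whatever its cause, goes to the trials unit within 24 hours and all are forwarded to the drug manufacturer (11.3). The Chief Investigator reviews each for causality and expectedness (11.4). Listed radiotherapy events keep the SAE timeframes (11.5), and the IDMC reviews accumulating toxicity (12.5). All of this stands, and it rules out several stronger conclusions a reader might draw:

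- *That serious radiotherapy harm goes unreported.* Inside the window it does not.
- *That such an event can never become a SUSAR.* Figure 3 does not restrict relatedness to the drug, so the route is contradictory rather than plainly closed.
- *That listed events are expected at any severity.* Section 11.5 is silent on severity and does not say that it overrides 11.1.8. The defect is an unresolved conflict.
- *That the toxicity comparison between arms is generally biased.* Adverse events go on the CRF whatever their cause unless unequivocally due to progression (11.2), and labels such as expected or SUSAR remove nothing from the data. Only late events could be lost.
- *That the earlier bladder study sizes the problem.* Section 1.4 reports "three out of five patients experiencing grade 3 bladder toxicity" and a further patient with grade 3 bowel toxicity, but after 36Gy in 6 fractions to the whole bladder with a different drug. That counts no missed report here. The same section describes another urothelial study with no dose-limiting toxicity.

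The reply does not answer the late rule, the conflict between 11.5 and 11.1.8, or the mismatch of causality terms.

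**Conclusion.** The point holds in a limited form. The clearest gap is the late rule: as written, serious radiotherapy-related events are not captured from about 70 days after the last fraction in the shortest case, moving to 112 days after three cycles and 763 days after all 34. These figures assume on-schedule cycles, radiotherapy ending on day 21 and the section 11.3 wording; the alternative reading of section 11.1.5 moves the shortest case to 90 days. The documents give no rate of late radiotherapy events, so the number lost cannot be estimated.

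The other two parts are contradictions. The literal definitions leave radiotherapy-only unexpected SAEs without an expedited route, while neighbouring sections imply one. A listed event attributed to both treatments meets two expectedness rules with no order of precedence. The protocol should be amended, but the gap concerns expedited and late reporting, not SAE reporting as a whole.

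**What to change.** 1. In section 11.3, extend the rule for SAEs beyond 90 days to those related to study drug or trial radiotherapy, and align its starting point with section 11.1.5.
2. Reconcile sections 11.1.6, 11.1.7, 11.4 and Figure 3 so that they use one causality term and say how unexpected radiotherapy-related SAEs are escalated. Add a separate radiotherapy causality field to the SAE form. Correct the cross-reference in section 11.4.
3. Reconcile section 11.5 with section 11.1.8 by stating that listing an event does not override the severity test.

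The cost is protocol wording, one form field, and a few more SAE reports and reviews. No new visits are needed: section 8.8 already has disease status and survival follow-up every three months to two years after study entry and every six months thereafter.
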